### **Part 1B: BMS-986148 Administered QW for 3 Weeks and 1 Week Off**

Approximately 24 subjects will be enrolled in ascending dose cohorts. Part 1B may begin after determining the MTD or a tolerated dose below the MTD in Part 1A. The starting dose for Part 1B will be chosen by modeling active ADC concentration-time data from Part 1A and selecting a fractionated dose that provides similar exposure to that of the MTD or a tolerated dose below the MTD. In the event that concentration-time data are not available for modeling, the starting dose will be 1/3rd of the MTD or a tolerated dose below the MTD from Part 1A. In Part 1B, BMS-986148 is administered every week for 3 weeks and 1 week off in a 28 day cycle.

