#### **3.1.2 Dose Expansion (Part 2)**

The purpose of the cohort expansion will be to assess preliminary antitumor efficacy, expanded safety experience, and PD effects of BMS-986148. Additional subjects will be treated after the completion of Part 1A and/ or Part 1B, at the MTD, or at an alternative dose below MTD as agreed upon by the BMS Medical Monitor and investigators. Part 2 can begin before the completion of Part 1B as the Q3W dosing regimen is the intended regimen for Part 2. However, if the aggregate PK and safety data indicate similar safety but higher cumulative exposure with the QW dose schedule, this schedule may also be evaluated in Part 2 in an additional cohort of 25 to 26 subjects, once the MTD or a tolerated dose below the MTD is identified in Part 1B. Treatment doses in the cohort expansion groups will not exceed the MTD.

Five expansion cohorts will be restricted to these tumor types 1) mesothelioma 2) pancreatic 3) ovarian 4) NSCLC, and 5) gastric cancer. Enrollment in cohort expansion will be determined by the mesothelin expression of the archived tumor sample (or fresh tumor sample if archived sample is not available).

The enrollment in each expansion cohort will be guided by a Simon 2-Stage design framework (see [Table 8.1-1](#)) exploring efficacy in the following 2 populations: [REDACTED]

Anti-tumor activity will be assessed initially in approximately 12 to 15 evaluable subjects per tumor type (Stage 1) treated in each monotherapy cohort, with the option to stop enrolling in a cohort without an initial anti-tumor activity signal. The number of subjects needed for the Stage 1 review is guided by a Simon 2-Stage design as shown in Table 8.1-1 below for each tumor type with futility boundaries as follows: after Stage 1, if none of the first 15 evaluable subjects in the gastric or pancreatic cohorts, if  $\leq 2$  of the first 12 with mesothelioma, or  $\leq 1$  of the first 14 with NSCLC or ovarian cohort demonstrate clinical activity, enrollment in the cohort meeting criteria may be stopped for this population.

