Clinical Drug Supplies									
Dose Level Assignment		X							At the completion of screening procedures and eligibility determination.
BMS-986148 Administration			X			X	X		Those supplied by BMS.

a In the event multiple procedures are required at a single time point, the following is a list of procedures from highest priority to low: 1) ECG, 2) PK sampling, and 3) clinical labs.

b C1D4: ± 1 day.

c Ophthalmological examination: 8-point exam (visual acuity, pupils, extraocular motility and alignment, tonometry, visual field, external examination, slit lamp examination and fundoscopy) conducted at baseline and focused exams with visual acuity, slit lamp, and as indicated will be conducted at the end of Cycle 1 (pre-dose Cycle 2), every other cycle, EOT and as clinically indicated during the study.

d Cycle 1, Day 1: vital signs will be obtained before the BMS-986148 infusion and then every 15 minutes (± 5 minutes) until 60 minutes after completion of the infusion. During subsequent treatment visits, vital signs may be obtained every 30 minutes (± 10 minutes) until 30 minutes following completion of the last infusion. If any vital sign is abnormal at the final check, the subject must be observed further for a period of time, as clinically indicated. The start and stop time of the study drug infusion should be documented (start of drug infusion = 0 hour).

█ C: cycle; CBC: complete blood cell (count); CRF: case report form; D: day; █  
█ ECG: electrocardiogram; ECOG: Eastern Cooperative Oncology Group; EOI: end of infusion; EOT: end of treatment; IHC: immunohistochemistry; LVEF: left ventricular ejection fraction; MUGA: multigated acquisition; PE: physical examination; PK: pharmacokinetics; QTcF: QT interval corrected by Fridericia's formula; SAE: serious adverse event.

**Table 5.1-5: Cycle 2 to Off Study Visit, Part 1B (Weekly Dosing BMS-986148 Monotherapy Dosing / 28 Day Cycle) Procedural Outline (CA008002)**

Procedure a	C2 and C3				C4				C5 and Beyond			EOT	Follow-up (30 and 60 Days After Last Dose)	Survival Follow- up b	Notes	
	D1	D8	D15	D22	D1	D2	D4 c	D8	D15	D1	D8	D15		(±5 days)		(±2 weeks)
Safety Assessments																
Targeted PE	X	X	X	X	X						X			X	X	To include signs and symptoms of peripheral neuropathy and ocular toxicity. Any grade ocular toxicity requires ophthalmologist consultation and discussion with medical monitor as appropriate.

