## 5.5 Pharmacokinetic and Immunogenicity Assessments

Serum samples for total antibody, active ADC, [REDACTED] and nivolumab PK assessments as well as plasma samples for [REDACTED] unconjugated tubulysin PK assessments will be collected in all subjects. Serum samples for antibody-drug antibody (ADA) assessments will also be collected in all subjects. The PK parameters to be assessed include:

Cmax	Maximum observed serum or plasma concentration
Tmax	Time of maximum observed serum or plasma concentration
AUC(0-t)	Area under the concentration-time curve from time 0 to the time of the last quantifiable concentration
AUC(TAU)	Area under the concentration-time curve in 1 dosing interval
Ctau	Concentration in a dosing interval
Ctrough	Trough observed serum or plasma concentration (this includes pre-dose concentrations and Ctau concentrations)
CLT	Total body clearance calculated as Dose divided by AUC(TAU)
Vss	Volume of distribution at steady state
Vz	Apparent volume of distribution at steady state
AI_AUC	AUC accumulation index; ratio of AUC(TAU) at steady-state to AUC(TAU) after the first dose
AI_Cmax	Cmax accumulation index; ratio of Cmax at steady-state to Cmax after the first dose
AI_Ctau	Ctau accumulation index; ratio of Ctau at steady-state to Ctau after the first dose
Cavg	Average concentration over a dosing interval calculated by dividing AUC(TAU) by tau
T-HALF	Terminal serum or plasma half-life

Individual subject PK parameter values will be derived by noncompartmental methods using a validated PK analysis program. Actual times will be used for the analyses.

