**Table 5.5.1-2: PK and ADA Sampling Schedule for BMS-986148 Monotherapy QW Dosing Regimen**

Study Day of Sample Collection	Event	Time (Relative To Start of Infusion) Hour: Min	PK Sample (Serum and Plasma)	ADA Sample (Serum)
1	Predose	00:00	X	X
1	EOI	01:00	X	
1		04:00	X	
2		24:00	X	
4 a		72:00	X	
8	Predose	00:00	X	
8	EOI	01:00	X	
15	Predose	00:00	X	
15	EOI	01:00	X	
22		168:00	X	
Every 2 Cycles Starting at Cycle 5 (PK Only)				
1	Predose	00:00	X	
Every 4 Cycles Starting at Cycle 8 (PK and ADA)				
1	Predose	00:00	X	X
EOT			X	X
30-Day Follow-Up			X	
60-Day Follow-Up			X	X
Event Driven c			X	X

a EOI = Sample must be collected immediately following the end of the infusion. End of Infusion Serum will be collected for measuring total antibody, [REDACTED] and active ADC concentrations. Plasma will be collected for measuring [REDACTED] unconjugated tubulysin concentrations.

c In the event that labs are drawn and the subject is not dosed.

ADA: anti-drug antibody; ADC: antibody-drug conjugate; EOI: end of infusion; EOT: end of treatment; min: minimum; PK: pharmacokinetics; QW: every week.

**Table 5.5.1-3: PK and Anti-Drug Antibody Sampling Schedule for BMS-986148 Q3W Dosing Regimen in Combination with Nivolumab**

Study Day of Sample Collection	Event	Time (Relative to Start of Infusion) Hour:Min	BMS-986148 PK Sample (Serum and Plasma)	Nivolumab PK Sample (Serum)	BMS-986148 and Nivolumab ADA Samples (Serum)
Cycle 1					
1	Predose	00:00	X	X	X
1	EOI a	00:30		X	
1	EOI a	01:00	X		
1		04:00	X		
2 b		24:00	X	X	
4 ■		72:00	X	X	
8		168:00	X	X	
15		336:00	X	X	X
Cycle 2					
1	Predose	00:00	X	X	
1	EOI	00:30		X	
1	EOI	01:00	X		
Cycle 3					
1	Predose	00:00	X	X	X
1	EOI	00:30		X	
1	EOI	01:00	X		
Cycle 4					
1	Predose	00:00	X	X	X
1	EOI	00:30		X	
1	EOI	01:00	X		
1		04:00	X		
2 b		24:00	X	X	
4 ■		72:00	X	X	
8		168:00	X	X	
15		336:00	X	X	
Every 2 Cycles Starting at Cycle 5 (PK Only)					
1	Predose	00:00	X	X	

**Table 5.5.1-3: PK and Anti-Drug Antibody Sampling Schedule for BMS-986148 Q3W Dosing Regimen in Combination with Nivolumab**

Study Day of Sample Collection	Event	Time (Relative to Start of Infusion) Hour:Min	BMS-986148 PK Sample (Serum and Plasma)	Nivolumab PK Sample (Serum)	BMS-986148 and Nivolumab ADA Samples (Serum)
Every 5 Cycles Starting at Cycle 9 (PK and ADA)					
1	Predose	00:00	X	X	X
EOT			X	X	X

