## 7.7 Pharmacokinetics

PK parameters for the total antibody, [REDACTED] active ADC, [REDACTED] and unconjugated tubulysin will be calculated using noncompartmental analysis. All available plasma/serum concentration-time data from subjects who receive BMS-986148 will be reported. All available derived PK parameter values will be included in the PK dataset and reported, but only subjects with adequate PK profiles will be included in summary statistics and statistical analysis.

PK analysis will be provided separately for each of the above analytes. In general, summary statistics will be tabulated for the pharmacokinetics parameters by dose, dose regimen, and study day for each select analyte. To assess the attainment of steady state geometric mean Ctrough values will be plotted versus study day by dose and dose regimen.

Exploratory assessment of dose proportionality for total antibody, [REDACTED] and unconjugated tubulysin will be performed based on the power model described by Gough et al.

$$\text{PK Parameter} = A * \text{Dose}^{\beta},$$

which be estimated by the simple linear regression of the natural log of the PK Parameter (Cmax, AUC(TAU)) on the natural log of Dose:

$$E[\log(\text{PK Parameter})|\text{Dose}] = \alpha + \beta * \log(\text{Dose}).$$

A slope ( $\beta$ ) equal to 1 would indicate perfect dose proportionality. For each PK parameters (Cmax, AUC(TAU)), the point estimates and 90% CI of the slopes will be provided. Note that dose proportionality analysis may not be performed if there are two few different doses under some dose regimen, e.g., for the QW dosing for three weeks with one week off.

[REDACTED]

A population pharmacokinetic analysis may be conducted, which would be presented in a separate report.

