**Figure:**

- Plot of individual Ctrough and their geometric mean at each cycle for each dose + dose regimen group.
- Scatter plot of AUC(TAU) vs dose in log-log scale by regimen and superposed with the regression line from the power model. Regression line's mathematical equation is also shown in the figure.
- Scatter plot of Cmax vs dose in log-log scale by regimen and superposed with the regression line from the power model. Regression line's mathematical equation shown in the figure.

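### Weekly regimen: the steady-state trough displays put 7-day and 14-day troughs together, and the two schedules disagree on a Cycle 4 Day 22 PK sample (minor)

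*SAP*

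**What the plan says.** **Dosing.** Protocol Section 3.1.1 states: "In Part 1B, BMS-986148 is administered every week for 3 weeks and 1 week off in a 28 day cycle". Doses fall on Days 1, 8 and 15, so the next Day 1 dose comes 14 days after the last one.

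**Trough definition.** Protocol Section 5.5 defines Ctrough as "Trough observed serum or plasma concentration (this includes pre-dose concentrations and Ctau concentrations". SAP Section 4.2.1 says the same. Neither limits the time since the last dose.

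**Steady-state displays.** The text of SAP Section 7.7 states: "To assess the attainment of steady state geometric mean C trough values will be plotted versus study day by dose and dose regimen". The figure list of the same section asks for: "Plot of individual Ctrough and their geometric mean at each cycle for each dose + dose regimen group". Neither separates samples by time since last dose.

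**PK sampling.** Protocol Table 5.5.1-2 ("PK and ADA Sampling Schedule for BMS-986148 Monotherapy QW Dosing Regimen") gives these post-dose troughs:

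- Cycle 1: Days 8 and 15 pre-dose, and Day 22 at 168 h
- Cycle 2: none
- Cycle 3: Day 1 pre-dose
- Cycle 4: Days 1, 8 and 15 pre-dose, and Day 22 at 168 h
- Cycle 5 onward: Day 1 pre-dose only, at the listed cycles

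**Visits.** Protocol Table 5.1-5 ("Cycle 2 to Off Study Visit, Part 1B (Weekly Dosing BMS-986148 Monotherapy Dosing / 28 Day Cycle) Procedural Outline") has a Day 22 column for Cycles 2 and 3. Its Cycle 4 columns are Days 1, 2, 4, 8 and 15.

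**The concern.** A trough series shows attainment of steady state only if each point has the same position in the dosing pattern. Here Cycle 1 supplies only 7-day troughs, Cycle 3 and Cycles 5 onward only 14-day troughs, and Cycle 4 both. A change between adjacent points can therefore come from the week off rather than from accumulation or its absence. A reader could see a fall where exposure is stable, or miss accumulation that is taking place. The judgement matters because the three accumulation indices (AUC, Cmax and Ctau) are ratios to values at steady state.

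The scheduling conflict is a separate matter. The protocol synopsis takes PK parameters from Cycles 1 and 4, and Day 22 is the only 7-day sample after the third dose of Cycle 4. A site that works from the visit table alone could miss it.

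**Working it through.** The documents give no figure on this point, so there is none to reproduce. The check classifies each sample by gap and then estimates the size of the artefact.

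**Step 1: gap since last dose.** Days 8, 15 and 22 follow the doses of Days 1, 8 and 15 by 7 days. Day 1 of a later cycle follows the Day 15 dose by 29 − 15 = 14 days.

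**Step 2: model and inputs.**

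- Half-life of total antibody: protocol Section 3.3.1 (reproductive status) equates 5 half-lives with about 60 days, so 60/5 = 12 days.
- Half-lives for active ADC and unconjugated tubulysin are not given in the visible text. Values below 12 days are assumptions.
- One compartment, equal unit doses, superposition. The fraction left after 7 days is r = 2^(−7/12) = 0.667.

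Formulas, with T the Day 1 pre-dose level of a cycle (zero in Cycle 1):

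- Day 8 = r(1 + T); Day 15 = r(1 + Day 8); Day 22 = r(1 + Day 15)
- next Day 1 = r × Day 22

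| Cycle | Day 1 (14-day) | Day 8 (7-day) | Day 15 (7-day) | Day 22 (7-day) |
|---|---|---|---|---|
| 1 | – | 0.667 | 1.113 | 1.410 |
| 3 | 1.128 | not sampled | not sampled | not sampled |
| 4 | 1.165 | 1.445 | 1.632 | 1.757 |
| 5 | 1.172 | not sampled | not sampled | not sampled |

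**Step 3: the study-day plot.** Each plotted mean has a single gap, but adjacent points do not:

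- Cycle 1 Day 22 to Cycle 3 Day 1: 1.128/1.410 = 0.80, a 20% fall.
- Cycle 4 Day 22 to Cycle 5 Day 1: 1.172/1.757 = 0.67, a 33% fall.
- Matched by day, Cycle 4 Day 8 against Cycle 1 Day 8: 1.445/0.667 = 2.17, a real rise.
- Matched Day 1 troughs: 1.128, 1.165, 1.172, a plateau.

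**Step 4: the per-cycle mean, if days are pooled.** Pre-dose samples only, leaving out the zero before the first dose:

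- Cycle 1: (0.667 × 1.113)^(1/2) = 0.86
- Cycle 3: 1.13
- Cycle 4: (1.165 × 1.445 × 1.632)^(1/3) = 1.40
- Cycle 5: 1.17

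The change from Cycle 4 to Cycle 5 is 1.172/1.40 = 0.84, a 16% fall. With Day 22 counted as a Ctau value, the Cycle 4 mean is (1.165 × 1.445 × 1.632 × 1.757)^(1/4) = 1.48 and the fall is 1 − 1.172/1.48 = 21%. The Day 1 trough over the same step is flat.

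**Step 5: sensitivity to half-life.** At an assumed 6 days the pooled pre-dose means run 0.54, 0.34, 0.52, 0.34 for Cycles 1, 3, 4 and 5. At true steady state the Day 1 trough is 0.67, 0.45 or 0.25 of the Day 22 trough for half-lives of 12, 6 or 3.5 days.

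**Step 6: the two Cycle 4 schedules.** The PK table has a Day 22 row at 168 h; the visit table's Cycle 4 columns end at Day 15. The visit table does refer PK sampling to Section 5.5.

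**Step 7: the end of Cycle 1.** The weekly PK table has no Cycle 2 sample, so nothing is drawn at the end of week 4. Weekly starting levels are 1, 1.67, 2.11 and 1.41, so week 4 holds 1.41/(1 + 1.67 + 2.11 + 1.41) = 23% of Cycle 1 AUC(0–28 d) at 12 days. At assumed half-lives of 6 and 3.5 days the share is 15% and 8%.

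**The case against.** Much of the case on the other side stands.

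- **No study-day mean combines unlike samples.** Section 7.7 also summarises PK by study day and time. The like-for-like Day 1 series is on the plot and shows the plateau to a reader who looks for it. Pooling within a point arises only if the figure list's mean at each cycle combines days, which it does not say outright. The 16% and 21% figures depend on that reading.
- **The protocol's own wording is more favourable.** Section 8.4.4 plots geometric mean minimum concentration. For this regimen that is naturally the Day 1 value after the week off. The SAP uses Ctrough instead.
- **Other conventions are not visible.** The SAP defers to a PK harmonization document and a data presentation plan, which might hold display rules or define tau for the weekly regimen.

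A reader might also infer three stronger things that the documents do not support:

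- **That the Part 2 regimen choice rests on this plot.** Protocol Section 3.1.2 refers to aggregate PK and safety data indicating "similar safety but higher cumulative exposure with the QW dose schedule", after which the weekly schedule may also be tested. No text links that choice to the trough display.
- **That the Cycle 4 Day 22 sample has been dropped.** The visit table's pointer to Section 5.5 keeps it required. The fault is a conflict between tables.
- **That Cycle 1 exposure is invalid.** No listed parameter is a 28-day AUC, and AUC(TAU) covers one dosing interval. If tau is 7 days, the interval after the Day 1 dose is sampled alike in Cycles 1 and 4. Cycle 4 is closed by the Cycle 5 Day 1 sample.

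What remains is that the SAP text does not tell the analyst to keep the two gaps apart, and that the two tables disagree.

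**Conclusion.** The point holds as a minor one. As written, the weekly trough displays can show the week off as a change in trough. At a 12-day half-life the artefact along the axis is a fall of 20% to 33% between adjacent points. It is 16% to 21% between Cycles 4 and 5 if the per-cycle mean pools days. The matched Day 1 trough moves only from 1.165 to 1.172. These sizes rest on a one-compartment model, equal doses given on schedule, and the total-antibody half-life; shorter half-lives are assumed and make the artefact larger. It is a risk of misreading steady state, not a demonstrated error, in a part of about 24 subjects, plus 25 to 26 more if a weekly cohort opens in Part 2. The Cycle 4 Day 22 mismatch is a plain contradiction between two tables and needs no assumption.

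**What to change.** 1. **SAP Section 7.7, text and figure list, weekly regimen.** Show and summarise two series: 14-day troughs (Day 1 pre-dose, Cycle 3 onward), and 7-day troughs (Days 8, 15 and 22, matched by day, Cycle 1 against Cycle 4). Do not pool them within a cycle, and judge steady state within each series. Matching by day is needed because 7-day troughs also rise from Day 8 to Day 22 within a cycle. Cost: SAP wording only.
2. **Protocol Tables 5.1-5 and 5.5.1-2.** Reconcile them for Cycle 4 Day 22. If the sample stays, the visit table needs the column; if not, the PK row goes and the 7-day series is matched on Days 8 and 15. Cost: one table edit, with no sampling beyond what the PK table already requires.
3. **Optional, not required.** A Cycle 2 Day 1 pre-dose PK sample would close week 4 of Cycle 1, at a visit that already has laboratory tests. It matters only if 28-day Cycle 1 exposure is to be compared with the Q3W regimen, whose PK table already has a Cycle 2 Day 1 pre-dose sample. Cost: one draw per weekly subject.

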**Summary:**

Summary statistics will be provided for the following all listed parameters in [Section 4.2.1](#) by dose, dose regimen, study day and time.

Geometric means and coefficients of variation will be presented for all parameters after the first dose except Tmax and T\_HALF. Median, minimum, and maximum will be presented for Tmax, T\_HALF.

**Figure:**

- Plot of individual Ctrough and their geometric mean at each cycle for each dose + dose regimen group.
- Scatter plot of AUC(TAU) vs dose in log-log scale by regimen and superposed with the regression line from the power model. Regression line's mathematical equation is also shown in the figure.
- Scatter plot of Cmax vs dose in log-log scale by regimen and superposed with the regression line from the power model. Regression line's mathematical equation shown in the figure.

**Listing:**

- All individual PK parameters will be listed including any exclusions and reasons for exclusion from summaries

## 7.8 Biomarker Analyses

Due to the exploratory nature of this study, analyses listed below may or may not be performed depending on data availability (some exploratory measurements in the study may be subject to change as technologies and assay methods evolve). Additional types of analyses may be conducted on a post-hoc basis pending review of data. Not all exploratory analyses will be included in the Clinical Study Report (CSR) unless they represent meaningful findings or are relevant to subject management.

**Summary:**

- Summary statistics (e.g., mean, median, minimum value, maximum value, standard deviation) will be provided for: (1) [REDACTED] CA125 and CA19-9; (2) change and percent change from baseline in [REDACTED] CA125 and CA19-9. Those analyses will primarily be grouped by dose and dose regimen. When applicable, similar analyses will be conducted by cohort.

**Figure:**

- Subject level longitudinal trend plot by cohort for [REDACTED] CA125 and CA19-9.

- Individual subject percent change from baseline over time for [REDACTED] CA125 and C19-9 respectively.

## 8 CONVENTIONS

In general, EmBARC standard time windowing, imputation rules, and counting rules will be applied.

### 8.1 Decimal Places

The number of decimal places displayed in all listings will be determined by the number of decimal places in the raw data.

Unless otherwise specified, minimum and maximum will be reported to the precision as the data collected, one more decimal place for the mean and median, and two more decimal places for the standard deviation. The adjusted geometric mean, geometric mean ratio and the lower and upper limits of confidence interval will be displayed to three decimal places.

### 8.2 Pharmacokinetic Summaries

#### 8.2.1 *In-text Tables*

For in-text pharmacokinetic tables, coefficient of variation (%CV) will be reported as integers. For other statistics except for standard deviations, values of 100 or higher will be presented as integers, values of 10 - <100 will be displayed to one decimal place, and values of 1 - < 10 will be displayed to two decimal places. Values less than 1 will be displayed to three decimal places. Ratios will also be displayed to three decimal places. Standard deviations will be reported to a precision of 1 decimal place more than the mean.

#### 8.2.2 *Handling of Non-Quantifiable Concentrations*

For the summaries of serum concentration-time data, concentrations that are less than the lower limit of quantification (LLOQ) should be displayed as “< LLOQ” in the listings and be treated as missing in summary tables and plots. For the purpose of calculating PK parameters, other than Ctrough, pre-dose concentrations that are less than LLOQ and concentrations prior to the first quantifiable concentration that are less than LLOQ will be set to zero, and all other concentrations less than LLOQ will be set to missing.

Summary statistics for Ctrough concentrations, analyses of PD-concentrations and ECG-concentration relationships will be calculated by imputing values less than LLOQ as  $\frac{1}{2} * \text{LLOQ}$ . This imputation is done for Ctrough concentrations because it is treated like a PK parameter; the imputation is not done for Day 1 pre-dose concentrations. Individual Ctrough listings will display these concentrations as “< LLOQ.”

All available serum concentration-time data and derived pharmacokinetic parameter values will be included in the PK data set and listed accordingly.

